Intervention and Outcomes in Duarte Galactosemia

Protocol dated 1/27/2017

NCT02519504

Intervention and Outcomes in Duarte Galactosemia: Project Protocol

Background and Goals: Duarte galactosemia (DG) is an autosomal recessive genetic condition characterized by partial loss of galactose-1-phosphate uridylyltransferase (GALT), which results in partially impaired metabolism of the sugar, galactose (Fridovich-Keil, Gambello et al. 2014). Galactose is abundant in milk and also found at lower levels in many other foods. DG affects close to 1/4000 births in the US. Many affected infants are detected by newborn screening (NBS) for galactosemia because of their diminished GALT activity and/or elevated galactose metabolite levels in blood (Pyhtila, Shaw et al. 2015). However, there is currently no consensus on long-term outcome prognosis for these infants; some studies suggest children with DG might be at increased risk for developmental difficulties later in childhood (Powell, Van Naarden Braun et al. 2009, Lynch, Potter et al. 2015), but no adequately powered study has been reported to document or contradict this hypothesis. There is also no consensus on whether children with DG might benefit from dietary restriction of galactose, at least in the first year of life, generally achieved by switching the baby from milk to soy formula. Because of the uncertainty, some healthcare providers recommend that infants with DG drink soy formula rather than milk in their first year of life; others do not (Fernhoff 2010, Fridovich-Keil, Gambello et al. 2014). The goals of this project are to assess whether children with Duarte galactosemia, ages 6-12 years old, experience developmental disorders relative to controls, and if so, whether dietary exposure to milk in infancy or early childhood is associated with developmental outcomes in this patient population.

To achieve these goals we will conduct a large multi-state case-control observational study. In Part 1 of this study we will recruit cases and gather demographic and diet history for these children using an online or telephone parent-response survey. In Part 2 of the study we will conduct direct, non-invasive developmental assessments on a subset of cases enrolled in Part 1. We will also recruit and enroll the siblings of cases to participate as controls in Part 2. The Specific Aims of this study are to:

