In total, we may receive up to 10,000 completed surveys for Part 1 of this study. We expect that respondents will be distributed geographically among the collaborating states, and that, as infants, the cases will reflect the full spectrum of dietary galactose exposures. From a pilot study, we also expect that the vast majority of respondents will give permission to be re-contacted. Finally, for Part 1 of this study we have requested a waiver of written consent (consent will be online or verbal) because survey respondents will participate either online or by telephone, and a waiver of child assent because the online or telephone logistics of this part of the study will make meaningful assent impractical.

Part 2 of this study will involve direct assessments of child developmental outcomes of both cases and controls. These direct assessments will be conducted in Direct Testing Blocks (explained below) to be distributed geographically across participating states and conducted at different times throughout the 3 years of the funded project.

From among the survey respondents in Part 1 we will recruit at least 144 cases to participate in Part 2 of

the study. We may also recruit parents from among the Part 1 respondents to participate in focus groups or other related research studies. Of course, we will only attempt to re-contact Part 1 survey respondents who have given explicit permission to be re-contacted.

From the Part 1 survey responses we will know the ages and genders of candidate controls from these families (children ages 6-12 who do not have DG). We will recruit at least 144 controls from these families to participate in Part 2 of the study. The parent/guardian of each of these controls will be asked to complete a shortened version of the Part 1 survey for their child.

To determine the locations of specific Part 2 direct assessment blocks we will sort survey respondent families into geographic areas defined by a 2-hour driving radius from a hub. We will classify each area in terms of the numbers of candidate DG and unaffected sibling volunteers and will also note the diet histories of the cases and the genders and other relevant parameters. *Geographic areas will be selected as potential sites for direct testing blocks that include >24 eligible children (cases + controls).*

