As we tested multiple outcome measures for association with DG status (Aim 1) and for association with diet among DG cases (Aim 2), for each of the outcomes considered, we identified the relevant covariates to adjust for. Using the steps described below, we determined the subset of covariates to be included in subsequent models for each outcome.

- 1. Using the information provided in step #8 above, we identified all variables that were to be initially considered as potential confounders for each outcome measure.
- 2. With these variables as predictors and the outcome measure of interest as the response variable, we used the R package *glmnet* to fit a generalized linear model with lasso regularization.
 - a. We used 10-fold cross-validation to determine the optimal lambda value.
 - b. We identified the subset of variables with non-zero coefficients and flagged these as covariates for subsequent models of the outcome.
 - c. Please note: This approach assumed observations were independent and did not take into account the shared familial structure of the dataset. As described below, in later analyses we used a mixed-model approach to account for relatedness among family members in the study.

Dividing our full cohort into independent discovery and validation sets:

Although data on 73 outcome variables were collected, our study was only adequately powered to test ~20 hypotheses due to the need to correct for multiple testing. As we sought both to test phenotypic differences between DG cases and controls, and also to test phenotypic differences associated with diet among cases, this substantially reduced the number of phenotypes we could consider without compromising the power of the data set. In order to find a balance between our desire to maintain adequate statistical power and our obligation to find differences in the data wherever they might exist, we first divided our sample into independent "discovery" and "validation" sets. We used the discovery set to identify the 10 outcome measures of greatest interest (smallest p value). We then used this subset of outcomes for a focused analysis of the validation set at an appropriate Bonferroniadjusted significance threshold.

- 1. We randomly selected ~25% of Part 2 study subjects for assignment to the discovery set.
 - To ensure independence of the discovery and validation sets, siblings were always assigned to the same set.
- 2. We assigned the remaining 75% of study subjects to the validation set.

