- We repeated the random assignment process until an appropriate mix of DG cases/controls and dairy-exposed/non-exposed cases (close to original distribution in the full dataset) was achieved in each set.

Using the discovery data set to rank order outcome variables to test in the validation data set:

- In the discovery set, we fitted a mixed-effect regression model (linear, logistic, or ordinal) for each outcome variable that included DG status and all necessary covariates as predictors.
- 2. The mixed model approach allowed for clustering at the family level and therefore took into account relatedness among study subjects.
- 3. We ranked the models by resulting p-value for the DG status regression coefficient, and selected the 10 top-scoring outcomes between cases and controls.
- Even if no models showed significance at raw p<0.05 for association with DG, we choose the 10 outcomes with the smallest p-values.

Aim 1: Identify phenotypes associated with DG

1. We fit comparable models for the 10 outcomes showing the smallest p values in the

discovery set using data from the independent validation set.

2. Our goal was to identify any outcomes whose models showed significant association with DG status at the Bonferroni-adjusted p-value threshold ($\alpha = 0.05/20 = 0.0025$) in the validation set. There were none.

Aim 2: Identify phenotypes associated with diet among DG cases

While the random assignment process described above yielded a discovery set with a satisfactory number of both cases and controls to assume it was representative of the full study population, the number of dairy-exposed cases and non-exposed cases in the discovery set was not large enough to confidently consider it a representative sample. For this reason, we tested the same 10 outcome variables as above for association with diet among DG cases.

- 1. We filtered the discovery set generated as described above to include only DG cases.
- Using the discovery set, we fitted a mixed-effect regression model (linear, logistic, or ordinal) for each of the 10 selected outcome variables that included milk exposure and all necessary covariates as predictors.
- 3. Our goal was to identify any outcomes whose models showed significant association with diet among cases at a Bonferroni-adjusted p-value threshold ($\alpha = 0.05/20 = 0.0025$) in the discovery set. There were none.

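### The SAP names family as the only clustering level, so Aim 2 diet standard errors may be too small, and block or state differences may confound the diet estimate, if diet and outcome both cluster by testing block

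*SAP*

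**What the plan says.** **Clustering.** In the SAP section on ranking outcomes in the discovery set, step 2 reads: "The mixed model approach allowed for clustering at the family level and therefore took into account relatedness among study subjects". Covariate selection, step 2c, gives the same purpose: "in later analyses we used a mixed-model approach to account for relatedness among family members in the study". No block, site, state or tester term is named anywhere in the SAP.

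**Aim 2 model.** Step 2 under Aim 2 fits a mixed model, in cases only, "for each of the 10 selected outcome variables that included milk exposure and all necessary covariates as predictors". It does not restate the random effect. The covariates come from a lasso run separately for each outcome: "We identified the subset of variables with non-zero coefficients and flagged these as covariates for subsequent models of the outcome". The list of candidates is not given.

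**Measurement.** The Protocol's description of Part 2 says: "These direct assessments will be conducted in Direct Testing Blocks (explained below) to be distributed geographically across participating states". The blocks were to be held at different times over three years, in areas within a 2-hour drive of a hub that had more than 24 eligible children.

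**Exposure.** The Protocol's Background says "some healthcare providers recommend that infants with DG drink soy formula rather than milk in their first year of life; others do not". It also expects that "the cases will reflect the full spectrum of dietary galactose exposures".

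**Data set for Aim 2.** The SAP's opening summary places the diet analysis in the validation set. The steps under Aim 2 place it in the discovery set.

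**The concern.** In a cases-only model the family intercept acts only where a family has two or more enrolled cases. The documents do not say how many families do. Aim 1 is less exposed, because a case and a sibling control would ordinarily be tested in the same block, so much of any block effect cancels. Aim 2 has no such matching.

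Children tested together share a facility, a testing period and perhaps testers. They may also share follow-up providers, because recruitment ran through state newborn-screening programmes. If that makes both milk exposure and outcome more alike within a block than between blocks, there are two consequences:

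- A model without block overstates the information about diet, so intervals are too narrow and tests reject too often.
- A block or state difference in outcome can pass for a diet effect, or hide one.

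The second matters even when nothing is significant, because reassurance about milk rests on how large an effect the intervals exclude and on whether the estimate is free of area differences.

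**Working it through.** **1. The plan's own figures.** Per-test alpha is 0.05/20 = 0.0025, as stated under Aim 2. Counts agree: 206 + 144 = 350 and 87 + 263 = 350. The SAP gives no standard error, design effect or ICC to reproduce.

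**2. Inputs.**

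| Input | Value | Source |
|---|---|---|
| Cases in total | 206 | SAP opening summary |
| Discovery cases | 206 × 87/350 = 51.2 | Assumes a proportional split |
| Validation cases | 206 − 51.2 = 154.8 | Same |
| Blocks, J | 350/25 = 14 | Assumption; actual number not given |
| Cases per block, m | 154.8/14 = 11.06; 51.2/14 = 3.66 | Arithmetic, equal blocks |
| Outcome ICC, ρy | 0.02 to 0.10 | Assumption |
| Diet ICC, ρd | 0.1 to 0.5 | Assumption |

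**3. Formula.** For a regressor in clustered data, DEFF = 1 + (m − 1)ρdρy. The correct standard error is √DEFF times the one from a model without block. The true two-sided alpha is 2[1 − Φ(3.023/√DEFF)], since 3.023 is the normal critical value for 0.0025 (two-sided testing assumed).

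| Set | ρy/ρd | DEFF | SE factor | True alpha |
|---|---|---|---|---|
| Validation | 0.02/0.1 | 1 + 10.06 × 0.002 = 1.020 | 1.01 | 0.28% |
| Validation | 0.05/0.3 | 1 + 10.06 × 0.015 = 1.151 | 1.07 | 0.48% |
| Validation | 0.10/0.5 | 1 + 10.06 × 0.050 = 1.503 | 1.23 | 1.37% |
| Discovery | 0.02/0.1 | 1 + 2.66 × 0.002 = 1.005 | 1.00 | 0.26% |
| Discovery | 0.05/0.3 | 1 + 2.66 × 0.015 = 1.040 | 1.02 | 0.30% |
| Discovery | 0.10/0.5 | 1 + 2.66 × 0.050 = 1.133 | 1.06 | 0.45% |

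**4. Simulation check.** With 14 equal blocks, no diet effect and no block term, simulated alpha at nominal 0.25% was:

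- about 155 cases: 0.41-0.52% at 0.05/0.3 and 0.89-1.3% at 0.10/0.5
- about 51 to 56 cases: 0.25-0.29% and 0.38-0.48%

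At nominal 5% it was 6.6-6.8% and 10.6-10.8% with about 155 cases, and 5.4% and 6.3% with 51. Since 100 − 6.8 = 93.2 and 100 − 10.8 = 89.2, a nominal 95% interval in the validation set would cover about 93% or 89%.

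**5. Sensitivity.** If ρd = 0, DEFF = 1 and nothing changes. At 0.10/0.5 with 155 cases the SE factor is 1.39 with 8 blocks and 1.10 with 30.

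**6. Cost of a block fixed effect, at ρy = 0.05 and ρd = 0.3.** Total diet variation is (1 − ρd)(n − 1) + ρd·m(J − 1). Within-block variation is (1 − ρd)(n − J). The outcome variance is 0.95 within block and 0.997 overall.

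- n = 155 (m = 11.07): (107.8 + 43.2)/98.7 = 1.530; × 0.95/0.997 = 1.458; square root 1.21.
- n = 51 (m = 3.64): (35.0 + 14.2)/25.9 = 1.900; × 0.95/0.997 = 1.810; square root 1.35.

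So the fixed effect raises the standard error by about 20% and about a third.

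**The case against.** Several points on the other side are sound.

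- **No ICC is documented.** Provider advice differs, but the Protocol does not say that advice sorts by state or testing area, or how far families followed it. It expects the cases to span all exposures. If milk exposure varies mainly within blocks, the problem vanishes. A reader might infer that diet followed state practice and that the standard errors are too small; the documents support neither as fact.
- **The outcome ICC may be small.** Instruments are standardised, testers are trained and blinded to diagnosis, and some scores are already normed.
- **Block or state may have been a covariate.** The candidate list is not given, so absence is unproven, and a lasso would tend to keep a block strongly related to outcome. This is only a tendency. The lasso selects on prediction of the outcome and, by the SAP's own note, treats observations as independent, so nothing secures a design feature in the model.
- **The result was null.** Under Aim 2 the SAP reports no outcome below 0.0025. Too-small standard errors produce false positives, and there were none. A reader might infer that the null is unsafe for this reason; widening the intervals around the same estimates would leave it unchanged. Confounding is different, because it could move the estimates, but the documents give no evidence that it did.
- **Size depends on the sample.** Working from all 206 cases (206/14 = 14.7 per block) gives larger inflation, but no Aim 2 analysis in the SAP uses 206. In the discovery set the inflation is slight at moderate ICCs.

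**Conclusion.** The point holds conditionally. Family is the only clustering the SAP names, testing was planned in geographic blocks, and any block covariate would depend on the lasso keeping it. Whether this understated the Aim 2 standard errors depends on two ICCs and a block count that the documents do not give.

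Under the assumptions shown, the true alpha at nominal 0.25% is about 0.5-1.2% in the validation set and about 0.25-0.5% in the discovery set for the two higher ICC settings, and close to nominal for the lowest. The size cannot be narrowed until the SAP's two statements about the Aim 2 data set are reconciled.

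The reported absence of Aim 2 findings would not be overturned by wider standard errors alone. What is at stake is honest interval width and an unexamined route for block or state confounding. This is a worthwhile improvement to the analysis and does not show that the conclusion is wrong.

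**What to change.** 1. Reconcile the SAP's opening summary with the steps under Aim 2 on which data set the diet analysis used.
2. Add a random intercept for testing block to the Aim 2 models, alongside family where both can be estimated. With fewer than 4 cases per block in the discovery set, the family variance may not be estimable; say in advance what is done then.
3. Tabulate milk exposure by block or state. If it is similar across areas, the concern largely closes.
4. Report a block or state fixed-effect model as a sensitivity analysis only. It removes between-area confounding, which a random intercept does only in part.
5. State whether block or state was among the lasso candidates.

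**Cost.** The primary change is one model term, using testing-location data the study should hold. In simulations with 11 to 15 cases per block, adjusting for block brought the error rates back to about 5% and 0.25%. With few blocks, a random intercept may be estimated at or near zero in some fits, so expect it to remove most of any inflation and not necessarily all. It should widen intervals less than the fixed effect, whose cost of about 20% (155 cases) to a third (51 cases) on the standard error at ICCs 0.05/0.3 is why that model should not lead.

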How will we assess child social-emotional development? We will ask parents to complete the Child Behavior Checklist (CBCL) (Achenbach and Rescorla 2001) which provides summary scores on Internalizing, Externalizing, and Total problems as well as scores on symptom scales including depression, social problems, and aggressive behavior. To assess internalizing problems more directly, we will also ask each child to complete survey measures of depression and anxiety using the short forms of the Children's Depression Inventory-2 (Kovacs, 2010) the Revised Children's Manifest Anxiety Scale: Second Edition (RCMAS-2) (Reynolds and Richmond 2008), a self-report measure yielding a Total Anxiety score. Each measure should take about 5 minutes to complete.

Parents will be asked to complete the Social Skills Improvement System Rating Scales (SSIS) (Gresham and Elliott 2008). The SSIS provides standard scores on Social Skills and Problem Behavior, as well as scores on specific social skills (e.g., cooperation, assertion) and problem areas (e.g., hyperactivity, autism spectrum behaviors).

How will we assess child physical development? We will assess motor skills involving manual dexterity, static and dynamic balance, and catching and releasing a ball with the *Movement Assessment Battery for Children--*2nd Edition (MABC-2). The MABC-2 is the test most frequently used to diagnose developmental coordination disorder. Children scoring below the 5th percentile on the MABC-2 are considered to have a significant motor coordination disorder (Zwicker, Missiuna et al. 2012).

We will assess the possibility of tremors using *The Essential Tremor Rating Assessment Scale* (TETRAS) (Elble, Comella et al. 2012) that will be videotaped and scored by a tester with advanced training in kinesiology. In addition, [name], a member of the Tremor Research Group that developed the TETRAS and a long-time colleague of the PI, will independently score 10% of the videos for reliability calculation. One of the TETRAS tasks involves drawing Archimedes spirals. In the proposed

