Statistical Analysis Plan

for

Study Protocol

Intervention and Outcomes in Duarte Galactosemia

Principal Investigator [name]

IRB00081271

NCT02519504

Date 04/01/2019

Statistical Analysis Plan:

Our Statistical Analysis Plan, prepared in follow-up to multiple meetings of a "Data Analysis Subgroup" from our research team, is described below. In short, data were cleaned and relevant covariates were identified for each outcome. Next, our cohort of 350 volunteers (206 cases and 144 controls) was randomly subdivided into independent "discovery" (n=87) and "validation" (n=263) sets that were approximately balanced with regard to case/control composition and covariates. We then tested each of the 73 outcome variables collected for each subject for possible association with case/control status using data from the discovery cohort; though none met the bar for statistical significance after multiple test correction we simply ranked them by ascending p value. Finally, we tested the 10 outcomes with the smallest p values from this ranking for (a) possible association with case/control status in the validation set, and also (b) possible association among cases in the validation set with milk exposure in the first year of life. All statistical analyses were performed in R.

How the data were cleaned:

- 1. We imported study data from REDCap (PCORIDGStudy_R_2017-XX-XX_XXX.r) into R.
- We filtered subjects by participation status to include only those who completed both Part 1 and Part 2.
- 3. We filtered out subjects marked for exclusion from analysis (e.g. after testing we realized they should have been excluded).
- 4. We filtered out subjects whose DG status was unknown.
- 5. We created a new variable representing the highest education level of either parent/guardian.
- 6. We created a new ordinal variable for breast milk exposure.
 - Value (0, 1, 2, or 3) indicating the number of time intervals (birth to 1 month, 2 to 6 months, 7 to 12 months) during which the subject drank at least some breast milk.
- We created new variables for average ABERS latency values at each wave (i.e., average "aber_w1_lat" and "aber_st_w1_lat").
- 8. For each variable in the dataset we:

- a. Indicated category label: administrative variable, covariate, DG status variable, dairy exposure variable, or outcome variable.
- b. For covariates, we indicated whether the variable should be considered in Aim 1 (DG/non-DG analysis), Aim 2 (DG-only diet analysis), or both.

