- c. For outcome variables, we indicated whether the variable should be considered in Aim 1 (DG/non-DG analysis), Aim 2 (DG-only diet analysis), or both.
- d. For outcome variables, we indicated the general domain of development under which it belonged.
- e. For each outcome variable, we indicated whether it had already been adjusted to account for any covariates and, if so, which ones (e.g., assessment score already normed for age and gender).
- f. Indicated data source (Part 1 survey, Part 2 testing).
- g. Indicated variable type (continuous, ordinal, categorical, binary).
- 9. For each variable, we plotted all data points and looked for outliers.
 - a. For continuous variables, we used a threshold of ± 3 SD from the mean.
 - b. If found, we confirmed with the testing team whether the outlier was genuine or a scoring/data entry error.
- 10. We cleaned and aggregated sparse categorical covariate levels where needed.
- 11. We compared "missingness" among outcome measures between DG cases and controls.
 - a. We tested whether the proportion of DG cases missing data on a given outcome differed significantly from the proportion of controls missing that outcome data.
 - b. We used a chi-square test if the number missing was large (i.e., expected counts >5) or
 Fisher's exact test if the number missing was small (i.e., expected counts <5).
 - c. If the proportion of missing data was significantly different between cases and controls, we could either: (1) exclude that outcome from analysis, or (2) impute missing data conditional on phenotype [see *Statistical Analysis with Missing Data* by Little and Rubin].
- 12. We calculated summary statistics for variables (from both Part 1 and Part 2 sources) across:(1) all subjects, (2) non-DG subjects only, (3) DG subjects only, (4) dairy-exposed DG subjects only, and (5) non-dairy exposed DG subjects only.

- We used mean, SD, median, and IQR for continuous variables.
- 13. For continuous variables, we checked to see if they followed a normal distribution using the Shapiro-Wilk Normality test. For non-normally distributed continuous variables, we tried transformation to achieve normality. If a log or square-root transformation failed to work, we used an inverse-normal transformation.

Covariate selection:

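### The SAP ranks and tests logistic and ordinal outcomes on an unnamed coefficient p-value; if it is a Wald p-value, a binary outcome with few or no control events is heavily disadvantaged

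*SAP*

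**What the plan says.** The SAP's opening summary states "We then tested each of the 73 outcome variables" for association with case/control status in the discovery set. The section on rank-ordering outcomes gives the model in step 1: "we fitted a mixed-effect regression model (linear, logistic, or ordinal) for each outcome variable". Step 3 gives the ranking rule: "We ranked the models by resulting p-value for the DG status regression coefficient". The 10 smallest p-values go forward whether or not any is significant. Under Aim 1, step 1 reads "We fit comparable models for the 10 outcomes showing the smallest p values", now in the validation set, and step 2 sets the threshold at 0.05/20 = 0.0025 and reports that no outcome met it. Aim 2 uses the same 10 outcomes, model types and threshold, with milk exposure as the predictor.

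The SAP does not say whether the p-value is Wald, likelihood-ratio or something else, and gives no rule for empty cells, separation or non-convergence in an outcome model. It does handle sparse data elsewhere, in the data-cleaning section: step 10 merges sparse levels of categorical covariates, and step 11b uses Fisher's exact test when few values are missing. Neither step covers the outcome models.

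**The concern.** A p-value attached to one regression coefficient most naturally means the Wald p-value in the model summary. A likelihood-ratio test compares two fitted models, and the SAP describes no such comparison. In a logistic model with few events, the Wald standard error grows faster than the estimate. When one group has no events the estimate diverges and the p-value goes to about 1, however many events the other group has.

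The ranking could therefore place a disorder seen only in children with DG below outcomes that show nothing. Specific Aim 1 in the protocol asks about increased risk of developmental disorders, and the SAP gives finding differences wherever they exist as a reason for the two-stage design. A ranking statistic that hides one pattern of difference works against both.

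**Working it through.** **Inputs.** From the SAP's opening summary: 206 cases + 144 controls = 350; discovery 87 + validation 263 = 350; 73 outcomes. From Aim 1: 0.05/20 = 0.0025, which reproduces exactly.

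**Assumptions.** The case share is the same in both sets: 87 × 206/350 = 51.2 and 263 × 206/350 = 154.8, so about 51 cases and 36 controls in discovery, 155 and 108 in validation. No covariates, independent children, two-sided tests, the other 72 outcomes null with uniform p-values, and Wald p set to 1 when a cell is empty. The prevalences are illustrative, because the documents give none.

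**Empty control cell, discovery.** Take 8/51 against 0/36. The maximised log-likelihood is 8 ln(8/51) + 43 ln(43/51) = −22.16 with DG status and 8 ln(8/87) + 79 ln(79/87) = −26.71 without it. The likelihood-ratio statistic is 2 × (26.712 − 22.156) = 9.11 on 1 df, p = 0.0025. The Wald p-value from an R logistic fit is 0.99. With a family random intercept (lme4 glmer), tables of this kind stopped with an error at default settings; other settings gave coefficient p-values of 0.95 to 0.997.

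**One control event, validation.** Take 15/155 against 1/108. The log odds ratio is ln(15/140) − ln(1/107) = −2.234 + 4.673 = 2.439. Its SE is √(1/15 + 1/140 + 1/1 + 1/107) = 1.041, so z = 2.34 and Wald p = 0.019. Likelihood ratio gives 0.0011 and Fisher's exact test 0.0029. At 30/155 against 1/108 Wald gives 0.0015, so 0.0025 can be reached once the cell is not empty.

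**How often the control cell is empty.** In discovery, 0.98^36 = 48% at a 2% control rate and 0.95^36 = 16% at 5%. In validation, 0.98^108 = 11% and 0.95^108 = 0.4%.

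**Enumeration over all 2×2 tables.** The chance of a top-10 place is the probability that the 10th smallest of 72 uniform p-values exceeds the observed p, a Beta(10, 63) tail. Validation power is P(p ≤ 0.0025). The chance of passing both stages is the product, because the sets are independent.

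| Controls v cases | Top 10: Wald / LR | Validation power: Wald / LR | Both: Wald / LR |
|---|---|---|---|
| 2% v 10% | 10% / 60% | 1% / 42% | 0.1% / 25% |
| 5% v 15% | 31% / 55% | 15% / 38% | 5% / 21% |
| 10% v 25% | 59% / 64% | 48% / 58% | 28% / 38% |

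**Check with family clustering.** A small simulation of the discovery set (150 replicates, random-intercept logistic model, family SD 1 on the logit scale) gave top-10 entry of 32% by Wald and 55% by likelihood ratio at 5% v 15%, close to the table.

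**Error of the likelihood-ratio test.** With equal prevalences of 2% to 10% it rejects at 0.0017 to 0.0038 against a nominal 0.0025. A null outcome enters the top 10 with chance 15% to 19%, against 10/73 = 14%. Part of its advantage in the table comes from this excess.

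**The case against.** The SAP never says Wald. If a likelihood-ratio p-value was used for the coefficient, the problem largely disappears. This stands, and it is why the point is conditional.

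No affected outcome is identified. The 73 outcomes are not listed, and the protocol's instruments mostly give scores, which would go into linear models. The step that records variable types, "Indicated variable type (continuous, ordinal, categorical, binary", applies to every variable and does not show that any binary outcome is sparse. A reader might take the protocol's sentence "Children scoring below the 5th percentile on the MABC-2 are considered to have a significant motor coordination disorder" as a ready example. It describes an instrument cut-off, and nothing says that this cut-off was one of the 73 outcomes. This objection also stands.

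A reader might infer that uncommon disorders linked to DG cannot reach 0.0025. That holds only if the validation set has no control events, which at a 5% control rate has a probability of 0.4%. Otherwise the result is reduced power.

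A reader might also infer that the test statistic partly produced the reported null. The documents do not support that. Power is limited under any test: Fisher's exact test passes both stages with chance 12%, 13% and 29% in the three scenarios of the table. Sample size, the 25/75 split and the small threshold account for much of the loss.

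What remains is that the SAP allows logistic and ordinal models, ranks and tests them on a coefficient p-value, and protects covariates and the missingness comparison from sparse counts but not the outcomes. A better-behaved test of the same models is readily available.

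**Conclusion.** The concern holds in conditional form. If the coefficient p-value is Wald, a binary outcome with no control events gets p near 1 or no fit, ranks at or near the bottom, and cannot pass 0.0025 where validation is empty too. Over the three scenarios, the chance of passing both stages falls from 25% to 0.1%, from 21% to 5%, and from 38% to 28%, compared with a likelihood-ratio test. The loss is small above about 10% control prevalence and absent for linear models.

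These figures rest on the proportional split, no covariates and independent children. Because the number and prevalence of sparse binary or ordinal outcomes are not given, the practical effect could be nil and the effect on the reported null is unknown. No size is given for Aim 2: the SAP's summary places the diet test in the validation set and its Aim 2 section places it in the discovery set, and the two must be reconciled first.

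**What to change.** State which test produced the p-values. If it was a likelihood-ratio test, saying so largely settles the point. If it was Wald:

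- For logistic and ordinal outcomes, in ranking step 3 and in the Aim 1 and Aim 2 tests, use a likelihood-ratio comparison of the same family mixed model with and without DG status (milk exposure in Aim 2). Keep coefficient tests for linear models.
- Tabulate event counts by group in each set for every binary and ordinal outcome, and state what happens when a model does not converge.
- Where a group has very few events, confirm the result with a penalised or exact method. Standard Firth regression has no family random effect, so it is a check and not a replacement.
- Re-rank the 73 outcomes, re-run the validation tests, and report whether the top 10 or any conclusion changes. Label this a post hoc sensitivity analysis, because the results are already known.
- Reconcile the two statements of which set was used for Aim 2.

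The cost is a small re-analysis with no new data. The downside is that the likelihood-ratio test is itself off nominal in sparse data, hence the confirmatory check.
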